Patient Information Sheet and Informed Consent

Official Title of the Study:

Knee Arthroplasty Surgery: Short-Term Effects of Robotic Assistance (ROSA).
Randomized Study.

Version: 3.0.

Date: March 20th, 2022

Principal Investigator: [name].

Site: Hospital Universitario Santa Cristina. Madrid, Spain.

Introduction

Total knee arthroplasty (TKA) is a common orthopedic surgical procedure. The survival rate of total knee prostheses is approximately 95% at 10 years and 90% at 15 years. Overall patient satisfaction is estimated at around 80%.

TKA failure is multifactorial, involving patient-related factors, implant design factors, and surgical technique. While patient-related risk factors and infection prevention protocols help reduce complications, current implant materials and designs are not a major cause of failure. Recent clinical series show that instability and malalignment are among the leading causes of early failure, which are primarily surgeon-dependent. Inadequate implant positioning, improper bone resection, or excessive or insufficient soft tissue release can be mitigated by improvements in surgical technique.

The goal of robotic assistance is to eliminate surgical inaccuracies and help execute the preoperative plan with precision. The robot positions and holds the cutting guide in place, assists with distal femoral cuts, determines prosthetic component sizes, and facilitates alignment and soft tissue balancing. The surgeon remains in full control of the saw and performs all bone cuts.

Robotic systems also enable intraoperative assessment of soft tissues, allowing the surgeon to implant the prosthesis in an anatomically adapted position, optimizing alignment and function. This increased precision may enhance early postoperative functional recovery compared to conventional TKA.

The ROSA surgical robot has been approved and commercially available since 2019. At Hospital Universitario Santa Cristina, the ROSA system has been used for TKA procedures since January 2021.

Objectives

Primary Objective:

To compare early functional recovery in patients undergoing TKA with robotic assistance versus conventional manual technique over the first three months after surgery.

Secondary Objectives:

- To analyze length of hospital stay, laboratory parameters, joint range of motion (ROM), and pain in both groups.

- To evaluate mechanical recovery following robotic and manual TKA.
- To compare postoperative long-leg standing radiographs in both groups.

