Materials and Methods

Study Design:

Prospective, randomized, controlled study involving two groups of patients undergoing TKA, all operated on by the same experienced surgeon skilled in both conventional and robotic-assisted techniques.

Patients will be selected from those on the hospital surgical waiting list who meet inclusion criteria. Selection is blind and conducted by the hospital's administrative service, independent of the principal investigator. Randomization will follow a parallel 1:1 model, using dice rolls.

Each group will include a minimum of 30 patients, enabling the use of parametric tests supported by the Central Limit Theorem.

Inclusion Criteria

- Patients with primary osteoarthritis indicated for TKA who provide informed consent.
- All patients will receive the same prosthesis model: Persona® (Zimmer Biomet), a posterior-stabilized primary knee prosthesis with patellar resurfacing, approved through public procurement.

Exclusion Criteria

- Previous surgery on the affected knee.
- Presence of other prostheses in the same limb.
- Hip pathology on the same side (e.g., dysplasia, avascular necrosis, arthrodesis, flexion contractures) that limits bone mass or mobility.
- Active infections near the affected knee joint.
- Obesity (BMI > 30).
- Dependent patients.
- Residents of long-term care facilities.
- Anatomical abnormalities, ligament instability, or severe femoral-tibial misalignment requiring alternative prosthesis models.

Surgical Protocol and Randomization

All patients will receive the same implant model: Persona[®] (Zimmer Biomet, Warsaw, Indiana, USA). Robotic-assisted surgeries will be performed with the ROSA[®] system (Zimmer Biomet, Warsaw, Indiana, USA).

After preoperative assessment, patients will be added to the surgical schedule. Scheduling occurs 15 days in advance and is managed by the department head. Once scheduled, randomization is performed using dice rolls:

- Even number: Robotic TKA (Group 1)
- Odd number: Manual TKA (Group 2)

Follow-up Schedule

All TKA patients at Hospital Universitario Santa Cristina are followed up weekly in outpatient clinics. First follow-up occurs at 2–3 weeks post-op; subsequent visits are at 2, 3, 6, 9, and 12 months. Annual visits continue for 5 years, then every two years until 10 years.

In this study, patients follow the same clinical follow-up schedule, although the study itself concludes at 3 months.

Variables

Demographic

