Age, sex, and comorbidities (diabetes mellitus, hypertension, rheumatoid arthritis, ischemic heart disease, anticoagulation).

Laboratory Parameters

Hemoglobin, hematocrit, ESR, CRP, and D-dimer levels will be recorded preoperatively, on the day of surgery (before and after the procedure), and at hospital discharge. Drain output (mL) during the first 24 hours post-op will also be recorded.

Surgical Parameters

Surgery duration (minutes), intraoperative complications (fracture, ligament or vascular injury), surgeon-performed bone cut corrections, and the difference (mm) between planned and robot-measured resections.

Pain

Assessed daily using a visual analog scale (VAS) during clinical rounds and recorded in the hospital's electronic medical record (HP-HCIS).

Length of Hospital Stay

Number of days from hospital admission for surgery to discharge, obtained from HP-HCIS.

Functional Recovery

Assessed using KOOS and SF-36 questionnaires preoperatively and at 2 and 3 months after surgery.

Joint Range of Motion

Measured daily with a goniometer and recorded in degrees of flexion and extension in the HP-HCIS.

Mechanical Recovery

Evaluated via surface electromyography (EMG) performed before surgery and at 3 months post-op using the Myomed 932 EMG device. Electrodes are placed over target muscle bellies, and both isometric (5-second contractions and rest, 1 minute) and isotonic (5 quick contractions and 5-second rest, 1 minute) protocols are performed. Peak and mean muscle strength are recorded.

Radiology

Preoperative AP/lateral X-rays and long-leg standing radiographs will be performed. Radiologic evaluation includes mechanical and anatomical axis, tibial slope, and osteoarthritis grade (Kellgren-Lawrence). Postoperative AP/lateral X-rays will be taken immediately post-op, at discharge, and at 2 and 3 months.

Data Management and Statistical Analysis

Data will be recorded in a coded database without personal identifiers. A separate confidential file linking study codes to patient identities (name, clinical ID, and national ID) will be kept by the principal investigator.

Patient outcomes will be analyzed over the 3-month period, comparing the evolution of each variable between groups. Descriptive statistics will be used, and group comparisons will be performed using Chi-square tests for binary variables. The CONSORT 2010 guidelines were followed in the preparation of the Methods section.

Ethical Considerations

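### Mechanical recovery is measured only by surface EMG but recorded as muscle strength; the data described support a statement about activation, and the preoperative value should enter as a covariate

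*Combined protocol and SAP*

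**What the plan says.** Under Secondary Objectives the plan lists: "To evaluate mechanical recovery following robotic and manual TKA". The Mechanical Recovery section gives one way of measuring it: "Evaluated via surface electromyography (EMG) performed before surgery and at 3 months post-op using the Myomed 932 EMG device". On the sensor it says only: "Electrodes are placed over target muscle bellies". The task is described as: "both isometric (5-second contractions and rest, 1 minute) and isotonic (5 quick contractions and 5-second rest, 1 minute) protocols are performed". The section then names the recorded variable: "Peak and mean muscle strength are recorded".

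For the analysis, the Data Management and Statistical Analysis section says: "Patient outcomes will be analyzed over the 3-month period, comparing the evolution of each variable between groups". The only test named there is Chi-square, for binary variables. The Study Design section adds: "Each group will include a minimum of 30 patients, enabling the use of parametric tests supported by the Central Limit Theorem". No model is given for EMG or any other continuous outcome.

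**The concern.** Skin electrodes record the electrical activity of muscle. They do not record force. The variable as named is therefore not the variable that the section describes. Because the plan compares the evolution of each variable between groups, the comparison as named would be one of muscle strength after robotic and manual surgery. A difference, or the lack of one, could then be read as a strength result on a stated secondary objective, although nothing described measures strength.

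The analysis is a second, smaller matter. EMG is taken before surgery and at 3 months, but the plan does not say how the preoperative value enters the comparison. Evolution could mean a change score, two values described side by side, or something else. The choice affects precision, and the most efficient standard option needs no further data.

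**Working it through.** **1. What is measured.** No arithmetic applies here, so the relevant statements are set side by side.

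| Item | What the plan gives |
|---|---|
| Objective | Mechanical recovery (Secondary Objectives) |
| Instrument | Surface EMG on a device called an EMG device |
| Sensor | Electrodes over target muscles, which are not named |
| Task | Isometric and isotonic contractions; no load, resistance, joint angle or reference contraction |
| Recorded variable | Peak and mean muscle strength, with no unit |
| Force, torque, dynamometer or manual strength grade | Not mentioned |
| EMG-to-force calibration or normalisation | Not mentioned |

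The strength sentence comes directly after the EMG protocol, and no other instrument is described to which it could refer. EMG amplitude also varies with electrode position, the tissue under the electrode, swelling and effort. Without calibration or a force reading, a change in amplitude from before surgery to 3 months cannot be read as a change in strength.

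**2. What baseline adjustment would gain.** The plan gives no figure to reproduce. Inputs:

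- n = 30 per arm, the stated minimum (Study Design).
- Two-sided alpha 5% and power 80%: assumed.
- Equal variance before surgery and at 3 months: assumed.
- Pre-post correlation r = 0.5 to 0.7: assumed.

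For a two-sample t-test of the 3-month value alone, the detectable difference is 0.736 SD. The normal approximation, (1.960 + 0.842) × √(2/30), gives 0.723; the t-distribution raises it to 0.736.

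Variance relative to the 3-month-only comparison:

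- Change score: 2(1 − r), which is 1.00 at r = 0.5 and 0.60 at r = 0.7.
- ANCOVA: 1 − r², which is 0.75 at r = 0.5 and 0.51 at r = 0.7.
- ANCOVA relative to change score: (1 − r²) / [2(1 − r)] = (1 + r)/2, which is 0.75 and 0.85.

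The detectable difference is 0.736 times the square root of the relative variance:

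| Analysis | r = 0.5 | r = 0.7 |
|---|---|---|
| 3-month value only | 0.74 SD | 0.74 SD |
| Change score | 0.74 SD | 0.57 SD |
| ANCOVA | 0.64 SD | 0.53 SD |
| Variance cut, ANCOVA against change score | 25% | 15% |
| Variance cut, ANCOVA against 3-month only | 25% | 49% |

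The single degree of freedom spent on the covariate is ignored; at this sample size it is negligible.

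**The case against.** **The plan never writes a strength conclusion.** The objective speaks of mechanical recovery, and the text says that strength is recorded, not that it will be claimed. This stands. A reader might infer that the trial has committed itself to reporting that one technique restores strength better or equally. The documents do not say so; the implication comes only from the variable's name.

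**The device may have a force channel.** The documents can neither confirm nor exclude this. It also stands, and the fix therefore leaves room for the sponsor to describe such a reading.

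**The baseline is not ignored.** A reader might infer that the plan compares raw 3-month amplitudes between patients. The evolution sentence, together with a preoperative recording, is more naturally read as change from baseline. The fair comparator is then the change score, and the gain from ANCOVA is 25% to 15%. The 49% figure applies only if the preoperative value is not used at all.

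**Randomisation already permits a comparison of amplitude.** Correct. What is in doubt is what amplitude is said to measure, not whether the arms can be compared. ANCOVA also does not remove electrode re-placement error or the effect of swelling at the second session.

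**Multiplicity.** Two protocols and two summaries give several results per muscle, and a reader might infer an uncontrolled false-positive rate. The plan states no confirmatory test or alpha for this secondary outcome, so the documents do not support calling this an error.

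**Conclusion.** The point holds in a limited form. The only measurement described for mechanical recovery is surface EMG, so the variable recorded as strength can support a conclusion about muscle activation and no more, unless a force reading exists that the documents do not describe. This rests on comparing the plan's own statements and on no numerical assumption.

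The analysis gain is modest and conditional. ANCOVA lowers the detectable difference from 0.74 to 0.64 SD at a correlation of 0.5, or from 0.57 to 0.53 SD at 0.7, against change scores, under the assumptions listed in the working. Those figures measure the benefit of specifying the analysis; they do not measure the labelling problem.

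The importance is low. One secondary objective is affected, and the primary objective, functional recovery assessed by KOOS and SF-36, is untouched.

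**What to change.** 1. Rename the variable peak and mean EMG amplitude (muscle activation), and limit the conclusion on mechanical recovery to activation. If the device gives a force reading, the sponsor should confirm this and describe its source and unit; the strength label may then stay for that reading.
2. Replace the unspecified comparison of evolution for this outcome with an ANCOVA of the 3-month value by randomised group, with the preoperative value from the same muscle and contraction protocol as covariate.

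Both changes are to wording and a standard model. They use recordings already planned and need no new patients, visits, staff or procedures. The downside is that, without a documented force reading, the trial can make no claim about strength.

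### The KOOS and SF-36 scores behind the primary objective have no stated between-group analysis, and nothing commits the trial to adjusting for the preoperative score it already collects

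*Combined protocol and SAP*

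**What the plan says.** Objectives gives the primary aim: "To compare early functional recovery in patients undergoing TKA with robotic assistance versus conventional manual technique over the first three months after surgery". Functional Recovery, under Variables, gives the instruments and times: "Assessed using KOOS and SF-36 questionnaires preoperatively and at 2 and 3 months after surgery".

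The comparative analysis is confined to two sentences in Data Management and Statistical Analysis. The first states the intent: "Patient outcomes will be analyzed over the 3-month period, comparing the evolution of each variable between groups". The second names the methods: "Descriptive statistics will be used, and group comparisons will be performed using Chi-square tests for binary variables".

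Study Design adds one general remark: "Each group will include a minimum of 30 patients, enabling the use of parametric tests supported by the Central Limit Theorem". Follow-up Schedule sets the end of the study: "In this study, patients follow the same clinical follow-up schedule, although the study itself concludes at 3 months".

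No section names a test or model for a continuous score, a KOOS or SF-36 score for the primary comparison, a primary visit, or any adjustment for the preoperative value.

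**The concern.** The one named test does not fit the outcomes that carry the primary objective. Chi-square could be applied to KOOS or SF-36 only after dichotomising them, and no cut-off is given. The remarks about parametric tests and about evolution could each mean several things: follow-up means, change from baseline, ANCOVA, or a repeated-measures model.

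Two separate things are at stake.

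- **Precision.** With a minimum of 30 per group it is limited. A comparison of follow-up means ignores the preoperative score. A change score subtracts all of it, which can add noise. Regression adjustment uses the score to the extent that it predicts the outcome.
- **Advance commitment.** While model, score and visit are open, they can be chosen after the results are known, and the nominal 5% error rate is then not protected.

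**Working it through.** **The plan's own figure.** The 30 per group cannot be reproduced, because no alpha, power, effect size or SD is given. Taken as it stands, with a two-sided 5% t-test, it has 80% power for a difference of 0.74 SD.

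**Inputs.** From the documents: 30 per group (a minimum), and scores before surgery and at 2 and 3 months. Assumed, because the documents are silent: two-sided 5%; true difference 0.5 SD of the follow-up score; no dropout; an exact 30/30 split; baseline/follow-up correlation r = 0.3, 0.5 or 0.7; ratio k = SDpre/SDpost = 0.8, 1 or 1.25.

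**Formulas.** The variance of the estimated difference is V × 2/30, in squared follow-up SDs:

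- follow-up means: V = 1, 58 df
- change score: V = 1 + k² − 2rk, 58 df
- ANCOVA: V = (1 − r²)(1 + 1/56), 57 df; the last factor is the expected cost of estimating the slope

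Power comes from the noncentral t with noncentrality 0.5/√(V × 2/30). For follow-up means, √(2/30) = 0.258 and 0.5/0.258 = 1.94, giving 47.8%. For ANCOVA at r = 0.5, V = 0.75 × 57/56 = 0.763 and the noncentrality is 1.94/√0.763 = 2.22, giving 58.7%.

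| Analysis at one visit | r = 0.3 | r = 0.5 | r = 0.7 |
|---|---|---|---|
| Follow-up means | 47.8% | 47.8% | 47.8% |
| ANCOVA | 50.7% | 58.7% | 75.2% |
| Change score, k = 0.8 | 42.4% | 54.7% | 75.2% |
| Change score, k = 1 | 36.3% | 47.8% | 69.1% |
| Change score, k = 1.25 | 29.3% | 38.3% | 56.1% |

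The 95% CI half-width is 0.52 SD for follow-up means and 0.50/0.45/0.37 SD for ANCOVA. Simulation agrees with the formulas to within 0.01.

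**Where ANCOVA does not gain.** There are two conditions, and they differ.

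- Against follow-up means, setting (1 − r²) × 57/56 = 1 gives r² = 1/57, so r is about 0.13. Below that ANCOVA loses at most 0.7 points (47.1% against 47.8% at r = 0).
- Against a change score, ANCOVA can fall behind when r is close to k. The loss is at most 0.8 points for k = 0.6 and 0.6 points for k = 0.8. None was found at k = 1 or 1.25 for r up to 0.9. Here the gain is largest at low r, the reverse of the first condition.

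**Two-visit alternative.** Assume the same 0.5 SD effect at both visits, equal SDs and a between-visit correlation of 0.7. The mean of the two follow-up scores has variance (1 + 0.7)/2 = 0.85, so the adjusted V is (0.85 − r²) × 57/56. Power is then 58/68/88%, against 51/59/75% for ANCOVA at 3 months alone. The order depends on the 2-month effect. At r = 0.5 the variance ratio is 0.60/0.75 = 0.8, so the average effect must exceed 0.5 × √0.8 = 0.447 SD, and the 2-month effect must exceed 2 × 0.447 − 0.5 = 0.39 SD, for the two-visit mean to be the more powerful.

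**Choosing afterwards.** Simulated with no true effect, each of the three single-visit analyses rejects about 5% of the time when fixed in advance. Reporting the smallest of the three p-values on one score and visit gives 8% to 11% over the ranges of r and k. Extending the choice to both visits gives 15% to 16% (equal SDs; assumed between-visit correlation 0.6/0.7/0.85).

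**The case against.** The strongest objection is that the wording already points to a longitudinal comparison. The objective runs over three months, and the analysis paragraph speaks of evolution. On that reading, making a 3-month ANCOVA primary would narrow the question and, under the two-visit assumptions above, give up about 7 to 13 points of power. This stands. A reader might infer that ANCOVA at 3 months improves at no cost on whatever the investigators intend. The documents do not support that, because a baseline-adjusted model of both visits is among the plans their wording allows. One visit or two is a trade-off for the investigators.

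A second objection concerns timing. The preoperative score must be unaffected by allocation. Surgical Protocol and Randomization puts the dice roll after preoperative assessment and scheduling, which is 15 days ahead, but the questionnaires are dated only by "Assessed using KOOS and SF-36 questionnaires preoperatively". They could therefore be completed after the dice roll. If knowledge of the allocation shifted the baseline difference by 0.2 SD, then at r = 0.5 and equal SDs ANCOVA would be biased by 0.5 × 0.2 = 0.10 SD, and follow-up means would not be. This also stands, and the fix must deal with it.

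Third, the false-positive figures do not argue for ANCOVA: fixing any single analysis in advance removes them. That is right, so they are kept separate.

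Finally, the exact 30/30 split is illustrative. Allocation is described by "Randomization will follow a parallel 1:1 model, using dice rolls", with no restriction. That does not weaken the case for adjustment, since unrestricted dice rolls do nothing to balance baseline scores.

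**Conclusion.** The gap is real and should be closed. The primary outcome has no specified analysis, and a covariate that is already being collected is not committed to use. Against follow-up means, single-visit ANCOVA gains about 3/11/27 points of power at r = 0.3/0.5/0.7. Against change scores at equal SDs it gains about 14/11/6 points. To match it, follow-up means would need 32/39/58 patients per group. The direction holds across the r and k examined, apart from the losses of under 1 point noted above. The size rests wholly on the assumed alpha, effect, correlation and SD ratio. No gain is claimed over a baseline-adjusted two-visit model, which can be more powerful if the effects are similar at both visits and less powerful if the 2-month effect is smaller.

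Three stronger readings should be resisted.

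- The documents do not specify a t-test, a change score or a dichotomised KOOS; they leave the matter open.
- Follow-up means and change scores are not invalid. Each is unbiased across randomisations and holds 5% error if fixed in advance, provided that a baseline used in the analysis precedes allocation.
- Nothing suggests that the investigators intend to pick the best result. The 8–11% and 15–16% are worst cases of leaving the choice open.

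**What to change.** Before outcomes are compared by arm, amend Data Management and Statistical Analysis to state that:

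- KOOS and SF-36 are compared between the randomised groups as continuous scores with the preoperative score as covariate, by ANCOVA at one visit or by a baseline-adjusted repeated-measures model over 2 and 3 months, reporting the adjusted mean difference and 95% CI;
- the primary comparison is one score named by the investigators, at one named visit or as the two-visit contrast, and the remaining scores and visits are secondary;
- the preoperative questionnaires are completed before the dice roll;
- Chi-square is used for binary variables only.

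The cost is a short amendment, one residual degree of freedom (57 instead of 58 for single-visit ANCOVA), and the loss from the ANCOVA of any patient without a preoperative score, as with a change score. Naming one primary score is also a scientific decision for the investigators. No further patients, visits or data are needed.
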